IRT	Interactive Response Technology
ITT	Intention-To-Treat
IUD	Intra-uterine Device
KFS	Kurtzke Functional System
MAR	Missing at Random
MCAR	Missing Completely at Random
MRI	Magnetic Resonance Imaging
MS	Multiple Sclerosis
MTR	Magnetization Transfer Ratio
NEDA	No Evidence of Disease Activity

NEPAD	No Evidence of Progression or Active Disease
CCI	CCI
CCI	CCI
CCI	CCI
ON	Optic Neuritis
PML	Progressive Multifocal Leukoencephalopathy
PY	Patient Years
RMS	Relapsing Multiple Sclerosis
CCI	CCI
CCI	CCI
RRMS	Relapsing Remitting Multiple Sclerosis
SAE	Serious Adverse Event
SD	Standard Deviation
SDMT	Symbol Digit Modalities Test
SmPC	Summary of Product Characteristics
SUSAR	Suspected Unexpected Serious Adverse Reaction
T1 Gd+	T1 gadolinium-enhancing
T25FW	Timed 25-Foot Walk
TB	Tuberculosis
TEAE	Treatment-Emergent Adverse Event
TIW	Three Times a Week
VZV	Varicella Zoster Virus
WOCBP	Women of Childbearing Potential

1 Synopsis

Clinical Trial Protocol Number	MS700568_0022
Title	A 2-year prospective study to evaluate the onset of action of Mavenclad® in subjects with highly active relapsing multiple sclerosis
Trial Phase	IV
IND Number	Not applicable
FDA covered trial	Not applicable
EudraCT Number	2017-002631-42
Coordinating Investigator	PPD [Redacted] Phone PPD Fax PPD
Sponsor	Merck KGaA [name] Medical Responsible: PPD PPD Phone: PPD
Sponsor Legal Representative in the European Union	Merck KGaA [name]
Trial centers/countries	Approximately 80 trial sites across Europe (including, but not limited to Austria, Belgium, Czech Republic, Finland, France, Germany, Hungary, Ireland, Italy, Poland, Spain, Sweden, the United Kingdom), as well as Australia, Canada and Israel.
Planned trial period (first subject in-last subject out)	First Patient First Visit: Q4/2018 Last Patient Last Visit: Q3/2021-2022
Trial Registry	ClinicalTrials.gov EU Clinical Trials Register

Objectives:

Primary Objective:

- To determine the onset of action of Mavenclad® in subjects with highly active relapsing multiple sclerosis (RMS)

Secondary Objective:

- To assess the effect of Mavenclad® on different immune system composites in particular cell subtypes count and repopulation

Tertiary Objectives:

- To assess the safety and tolerability of Mavenclad®
- To assess the effect of Mavenclad® on progression of disability, cognition and incidence of relapse
- CCI [REDACTED]

CCI [REDACTED]

Methodology:

This will be an open-label, single-arm, multicenter, 2-year Phase IV trial. Subjects meeting the eligibility criteria during a pre-baseline screening period of up to -3 months before baseline (Day 1 of treatment) will receive an initial treatment course in Year 1 and a retreatment course in Year 2.

Subjects will attend visits for assessments at end of Months 1,2,3,6, 12 following Baseline (Day 1 of treatment) and at end of Month 15,18, 24 following second treatment course (Month 1 of Year 2), respectively. Subjects will attend visits for blood sample as per mandatory monitoring at pre-Baseline and at Months 2, 6, 12, 14, 18 and 24. The primary endpoint(s) will be assessed during the first 6 months, secondary and tertiary endpoints will be assessed up to Month 24.

CCI [REDACTED]

Visit schedules for efficacy and safety assessments are detailed in the Schedule of Assessments.

Planned number of subjects: Approximately 265 subjects are planned to be included

Primary endpoint(s):

- Differences in the counts of combined unique active (CUA) MRI lesions during the first 6 months (i.e. during periods months 1-6, 2-6, 3-6) compared to baseline (i.e. the period screening to baseline)

Secondary endpoints:

- Characterization of immune cell subsets count at the end of 3, 6, 12, 15, 18 and 24 months compared to baseline

Tertiary endpoints:

Safety:

- Occurrences of treatment-emergent adverse events (TEAEs) and serious adverse events (SAEs) including and up to 24 months

Clinical:

- Changes in Symbol Digit Modality Test (SDMT) outcome at the end of 6, 12, 18 and 24 months compared to baseline
- Disability evolution as measured by Expanded Disability Status Scale (EDSS)/ Kurtzke Functional System (KFS), 9-Hole Peg Test (9HPT), Timed 25-Foot Walk (T25FW) at the end of 6, 12, 18 and 24 months compared to baseline
- Annualized Relapse Rate (ARR) between baseline and 24 months
- Changes in CUA lesions during the following post-baseline periods –compared to baseline period (i.e. the period from screening to baseline):
 - Period of month 6 to month 12
 - Period of month 1 to month 12
 - Period of month 18 to month 24
 - Period of month 1 to month 24Further periods and comparisons may be defined in the SAP
- Number of CUA lesions during the baseline and post-baseline periods as defined above
- Changes in active T1 gadolinium (Gd)+ lesion count at the end of 1, 2, 3, 6, 12, 15, 18 and 24 months compared to baseline
- Volume changes of T1 Gd+ lesions at the end of 1, 2, 3, 6, 12, 15, 18 and 24 months compared to baseline
- Number of T1 hypointense lesions at the end of 1, 2, 3, 6, 12, 15, 18 and 24 months compared to baseline
- Change in volume of T1 hypointense lesions at the end of 1, 2, 3, 6, 12, 15, 18 and 24 months compared to baseline
- Changes in new T2 lesion count during the post-baseline periods compared to the baseline period as defined above
- Responder rate during the different periods as defined above with responder being defined as subjects with a CUA lesion count reduction of at least 1
- Changes in T2 lesion volume at the end of 12 and 24 months compared to baseline
- Changes in Magnetization Transfer Ratio (MTR) at the end of 1, 2, 3, 6, 12, 15, 18 and 24 months compared to baseline
- Changes in brain volume at the end of 1, 2, 3, 6, 12 and 24 months compared to baseline (and changes at 24 months compared to 6 months to exclude pseudo-atrophy)
- No Evidence of Disease Activity (NEDA) at 24 months
- No Evidence of Progression or Active Disease (NEPAD) at 24 months

CCI

CCI

CCI

Safety assessments:

Safety assessments will include physical examination, including vital signs, laboratory tests, and reporting of adverse events (AEs) and SAEs.

Diagnosis and key inclusion and exclusion criteria

Key inclusion criteria:

- Male or female subjects \geq 18 years old
- Highly active RMS as defined by:
 - One relapse in the previous year and at least 1 T1 Gd+ lesion or 9 or more T2 lesions, while on therapy with other disease modifying drugs (DMDs)
 - Two or more relapses in the previous year, whether on DMD treatment or not
- EDSS score \leq 5.0

Key exclusion criteria:

- Previous exposure to drugs such as fingolimod, natalizumab, alemtuzumab, mitoxantrone and ocrelizumab
- Positive test for hepatitis C or positive tests for hepatitis B infection: either hepatitis B surface antigen (HBsAg) positive, or positive hepatitis B core antibody (total anti HBcAb) confirmed by a positive viral polymerase chain reaction (PCR)
- Current or previous history of immune deficiency disorders including a positive human immunodeficiency virus (HIV) result
- Currently receiving immunosuppressive or myelosuppressive therapy with, e.g., monoclonal antibodies, methotrexate, cyclophosphamide, cyclosporine or azathioprine, or chronic use of corticosteroids
- History of tuberculosis, presence of active tuberculosis, or latent tuberculosis
 - Presence of signs of PML detected by MRI, clinical and/or biomarker evaluations
- Active malignancy

Investigational Medicinal Product: dose/mode of administration/dosing schedule:

Mavenclad[®] 3.5 mg/kg body weight over 2 years, administered as 1 treatment course of 1.75 mg/kg per year. Each treatment course consists of 2 treatment weeks, one at the beginning of the first month and one at the beginning of the second month of the respective year. Each treatment week consists of 4 or 5 days on which a subject receives 10 mg or 20 mg (one or 2 tablets) as a single daily dose, depending on body weight.

Reference therapy: dose/mode of administration/dosing schedule: Not applicable

Planned trial and treatment duration per subject: The trial duration per subject will include: a pre-Baseline MRI assessment of up to 3 months and a 2-year treatment period.

CCI

Primary endpoint analysis:

Differences in the counts of CUA lesions will be evaluated using a mixed-effects linear model, accounting for within-center/region correlation through a hierarchical model. The differences in the counts of CUA lesions during the 3 periods compared to the baseline period will be tested in a sequential order starting with the latest period. The 3 hypotheses will be tested one-sided on a 2.5% significance level. The testing procedure will stop as soon as one of the hypotheses cannot be rejected following the pre-specified order. Due to this sequential order of tests an adjustment for a potential type-I-error due inflation due to the multiple testing is not required. The full analysis set (FAS) will be the primary population.

Safety analysis:

All safety assessments will be summarized descriptively by the treatment group for the safety population.

2 Sponsor, Investigators and Trial Administrative Structure

The Sponsor of this open label, single-arm, Phase IV trial with Mavenclad® is Merck KGaA, Darmstadt, Germany.

The trial will be conducted at approximately 80 sites in Europe (including but not limited to Austria, Belgium, Czech Republic, Finland, France, Germany, Hungary, Ireland, Italy, Poland, Spain, Sweden, the United Kingdom), as well as Australia, Canada and Israel.

The Coordinating Investigator, PPD [REDACTED] represents all Investigators for decisions and discussions regarding this trial, consistent with the International Council for Harmonization (ICH) Topic E6 Good Clinical Practice (GCP); hereafter referred to as ICH GCP. The Coordinating Investigator will provide expert medical input and advice relating to trial design and execution and is responsible for the review and signoff of the clinical trial report.

Signature pages for the Protocol Lead and the Coordinating Investigator as well as a list of Sponsor responsible persons are presented in [Appendix 14: Signature Pages and Responsible Persons for the Trial](#).

The trial will appear in the following clinical trial registries: ClinicalTrials.gov, EU clinical trials register.

A contract research organization (CRO) (PAREXEL International) will undertake the operational aspects of this trial with oversight by the Sponsor. Details of such structures and associated procedures will be defined in a separate Integrated Project Management Plan (IPMP).

The IPMP will be prepared by the CRO. Clinical quality assurance will be performed under the responsibility of the Development Quality Assurance department at Merck KGaA Darmstadt.

The investigational medicinal product (IMP) (cladribine) will be supplied by the Clinical Trial Supply Department of the Sponsor and packaged and labeled by Fisher Clinical Services.

Details of structures and associated procedures will be defined in a separate Manual of Operations, which will be prepared under the supervision of the Clinical Trial Leader.

3 Background Information

3.1 Multiple Sclerosis

Multiple sclerosis (MS) is a chronic, inflammatory, progressive, demyelinating disease of the central nervous system and is the most common cause of serious neurological disability in young adults (Przybek, 2015). The disease course of MS is heterogeneous and unpredictable requiring chronic treatment and regular medical monitoring by numerous methods such as for example, magnetic resonance imaging (MRI) that was designed for the investigation, diagnosis and management of patients with MS (Oreja-Guevara C, 2015).

MS is a neurological disorder characterized by inflammatory demyelination and neurodegeneration in the central nervous system. Eight percent of patients experience a highly active disease course with rapid and early disability often heralded by high relapse rates and early motor, cerebellar and/or cognitive dysfunction (Hirst CL, 2008). Early initiation of effective immunotherapy is considered to be important in this group of patients in order to prevent aggressive disease progression and severe disability accumulation (Dubey D, 2015).

3.2 Cladribine Tablets (Mavenclad®)

Despite the approvals of several newer therapies, the treatment burden of MS remains significant. The evidence for the effects of new therapies are weak and often of a short-term nature with little follow up of original trial participants (Tramacere, 2015).

It has been demonstrated that treatment with Cladribine Tablets in 2 short courses over 2 consecutive years has consistently shown robust clinically and statistically significant benefits in patients across the spectrum of relapsing remitting multiple sclerosis (RRMS) (early to late stages, treatment naïve or -experienced subjects) (Giovannoni, 2010; Leist, 2014). In particular, it was found that treatment with oral cladribine resulted in significant improvements in clinical and radiological efficacy outcomes, with significantly more patients remaining free from relapse, free from 3-month sustained expanded disability status scale (EDSS) progression and free from MRI lesion activity over 96 weeks compared to placebo (Giovannoni G, 2011).

Cladribine is indicated for the treatment of adult patients with highly active relapsing MS as defined by clinical or imaging features:

- patients with 1 relapse in the previous year and at least 1 T1 Gd+ lesion or 9 or more T2 lesions, while on therapy with other disease modifying drugs (DMDs),
- patients with 2 or more relapses in the previous year, whether on DMD treatment or not

Efficacy data from the CLARITY trial showed statistically significant improvements in the annualized relapse rate (ARR), proportion of patients relapse-free over 96 weeks, proportion of patients free of sustained disability over 96 weeks and time to 3-month EDSS progression in patient receiving cladribine 3.5 mg/kg compared to placebo (Giovannoni G, 2010). In addition, cladribine-treated group was statistically significantly superior to placebo with regard to number and relative reduction of T1 Gd+ lesions, active T2 lesions and combined unique active (CUA) lesions as demonstrated in brain MRI over the entire 96 weeks of the trial (Comi G, 2013).

3.3 Safety and Tolerability of Mavenclad®

The safety profile of Mavenclad® has been assessed in depth based on data from all studies of Mavenclad® in MS, including the long-term safety follow-up registry, and post-marketing data sources. Oral Mavenclad®, when administered as monotherapy at a cumulative dose of 3.5 mg/kg over 2 years, was well tolerated and demonstrated a manageable safety profile.

The comprehensive assessment of the safety data, after having accumulated more than 8,500 patient years (PY) of Mavenclad[®] exposure with up to 8 years of follow-up in some of the Mavenclad[®]-treated subjects, provides additional confidence of the safety profile of Mavenclad[®].

The important identified risks associated with Mavenclad[®] are severe lymphopenia, which is associated with the mechanism of action of the drug, herpes zoster and tuberculosis. Based primarily on the mechanism of action of Mavenclad[®], five important potential risks have been identified: severe infections, progressive multifocal leukoencephalopathy (PML), opportunistic infections (other than tuberculosis and PML), malignancies and teratogenicity/adverse pregnancy outcomes. The Sponsor will follow the proposed risk minimization measures specified in the summary of product characteristics (SmPC) of Mavenclad[®].

3.4 Risk-Benefit Assessment

The safety and tolerability of oral Mavenclad[®] in relapsing remitting MS have been demonstrated from the 2-year CLARITY trial followed by an additional 2.5 years of follow-up from the CLARITY-Extension (Cook S, 2016). While an oral formulation eliminates the adverse effects associated with frequent injections, Mavenclad[®] acts by depleting lymphocytes with a risk of developing opportunistic infections. The Sponsor have put in place adequate risk minimization measures for the participating subjects in this trial as well. Administering Mavenclad[®] will be restricted in subjects with lymphocyte count below normal in Year 1 and at least 800 cells/mm³ before initiating in Year 2. In addition, the lymphocyte count will be monitored at 2 and 6 months after each dosing schedule in Year 1 and Year 2. Subjects will be screened for latent TB infection as per local guidelines, as well as for Hepatitis B, Hepatitis C and human immunodeficiency virus (HIV) infection and will be excluded if found positive before each dosing schedule. The MRI scans will be evaluated by an expert to exclude any PML infection at screening and throughout the trial.

[figure not shown]
The risk-benefit relationship was carefully considered in the planning of the trial. The standard DMDs provide moderate efficacy and a low to moderate frequency of side effects. Second-line therapies for highly active MS are more effective, but associated with potentially severe side effects (Fazekas F, 2013). Mavenclad[®] is an oral drug approved in the treatment of highly active relapsing MS. Data from the CLARITY results suggest a clear benefit over placebo underlining the rationale for earlier treatment with cladribine tablets. In addition, data from CLARITY Extension indicates that treatment with cladribine tablets over 2 years, followed by 2 years of placebo, produced a durable clinical response (as measured from the end of CLARITY to the end of the Extension period). Importantly, there was no evidence of increased clinical activity (i.e., disease rebound) after treatment discontinuation (e.g. in the Cladribine 3.5 mg/kg switched to Placebo group), as reported for other therapies in MS with a direct effect on lymphocytes (Giovannoni G, 2017). The benefits of increased potential convenience and compliance with the unique posology of Mavenclad[®] will fill an unmet medical need in treating subjects with MS. The planned assessments for the trial are considered routine for monitoring MS disease progression and treatment outcomes. Standard of care will be provided to the subjects while undergoing the trial assessments to minimize clinical trial burden. MRI scanning with gadolinium enhancing contrast agents is routinely used for the identification and characterization of MS lesions (Rovira A, 2012). Monthly MRI assessment with gadolinium enhancing agent

have been used previously in Phase II trials with natalizumab (screening, Baseline and at the end of Months 1, 2, 3, 4, 5, 6, 9 and 12) (Miller, 2003) and fingolimod (Baseline and at the end of Months 1, 2, 3, 4, 5, 6 and 12) (Kappos, 2006); and in a Phase IIIb trial with interferon beta-1a (Baseline and at end of Months 1, 2, 3, 4, 5, 6, 7, 8, 9 and 10) (De Stefano, 2010). A recent assessment by European Medicines Agency's Pharmacovigilance Risk Assessment Committee (PRAC) concluded on the positive benefit risk outcome on gadolinium agents (gadobutrol, gadoteric acid and gadoteridol) with a recommendation to continue the use of such agents as per their current indications (EMA/424715/2017).

Based on the clinical and safety data available, the Sponsor considers that oral Mavenclad® has a positive benefit-risk profile that supports its use in the participating patient group. Therefore, the conduct of the trial specified in this protocol is considered justifiable. The trial will be discontinued in the event of any new findings that indicate a relevant deterioration of the risk-benefit relationship and would render continuation of the trial unethical.

Refer to the Mavenclad® SmPC for further information about the nonclinical and clinical programs and Guidance for the Investigators.

This clinical trial will be conducted in compliance with the clinical trial protocol, ICH GCP and any additional applicable regulatory requirements.

CCI

4 Trial Objectives

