5.4 Criteria for Initiation and Continuing of Trial Treatment

The lymphocyte count must be within normal limits before initiating treatment in Year 1, and at least 800/mm³ before initiating treatment in Year 2. If necessary, the treatment course in Year 2 can be delayed for up to 6 months to allow for recovery of lymphocytes. If this recovery takes more than 6 months, the subject will not receive the trial treatment anymore.

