5.5 Criteria for Subject Withdrawal

5.5.1 Withdrawal from Trial Therapy

Withdrawal may be considered in the following cases:

- Any subject that does not fulfil the above-mentioned criteria (Section 5.4) for the first and/or the second course of treatment
- Occurrence of latent infection such as herpes zoster, hepatitis or tuberculosis reactivation. In this case adequate anti infection treatment should be initiated and withdrawal from or delay of second course of Mavenclad® should be considered

If recovery from lymphopenia and/or infectious disease takes more than 6 months, the subject should not receive the second treatment course of Mavenclad®.

Withdrawal is mandatory in the following cases:

- Withdrawal of consent
- Protocol violation, including non-compliance that, in the opinion of the Investigator or Sponsor necessitates the subject being removed. The decision to withdraw the subject should be taken in consultation with the Medical Monitor
- Lost to follow-up
- Pregnancy
- Live or live attenuated vaccine at any time during the trial duration (except anti-herpes prophylaxis following a drop in lymphocyte count below 200 cells/mm³)
- Initiation of treatment with an experimental drug
- Initiation of treatment with another disease modifying therapy for multiple sclerosis
- Occurrence of active malignancies
- Presence of signs of PML detected by MRI, clinical and/or biomarker evaluations
- Occurrence of an exclusion criterion that is clinically relevant and affects the subject's safety, if discontinuation is considered necessary by the Investigator and/or Sponsor
- Lymphocyte count less than 800 cells/mm³ for more than 6 months before initiation of second treatment course
- HIV infection, active tuberculosis and active hepatitis before initiation of second treatment course
- Any events that unacceptably endanger the safety of the subject

If a subject is lost to follow-up, every possible effort must be made by trial center personnel to contact the subject and determine the reason for discontinuation. The measures taken to follow-up must be documented. If a subject discontinues before completion of trial procedures, the reason for discontinuation must be documented in the case report form (CRF) and source documents.

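### Section 3.4 says latent-TB positives are excluded before each course, but the rules that govern Course 2 leave a Month 12 latent-TB positive to judgement

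*Protocol*

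**What the plan says.** Section 3.4 of the protocol describes screening for latent TB, hepatitis B, hepatitis C and HIV, and states that subjects "will be excluded if found positive before each dosing schedule". No condition is attached, and the wording covers Course 2 as well as Course 1.

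The rules that control Course 2 are elsewhere:

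- **Section 5.4** requires a lymphocyte count of "at least 800/mm³ before initiating treatment in Year 2" and sets no infection criterion. The footnote to the Month 12 visit (7.1.8) does the same, although a TB test is on that visit's list.
- **Section 5.5.1, mandatory withdrawal**, includes "HIV infection, active tuberculosis and active hepatitis before initiation of second treatment course". Latent TB is not named. The same list takes in an exclusion criterion that arises during the trial, but only "if discontinuation is considered necessary by the Investigator and/or Sponsor". It ends with "Any events that unacceptably endanger the safety of the subject".
- **Section 5.5.1, optional withdrawal**, includes "Occurrence of latent infection such as herpes zoster, hepatitis or tuberculosis reactivation", in which case "adequate anti infection treatment should be initiated and withdrawal from or delay of second course of Mavenclad® should be considered".
- **Section 5.5.1, time limit**: "If recovery from lymphopenia and/or infectious disease takes more than 6 months, the subject should not receive the second treatment course".

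Latent TB is part of exclusion criterion 7 at entry (5.3.2). It is tested again before Year 2 dosing (Section 5.2; Table 3 in 7.4.3; Appendix 1).

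**The concern.** Section 3.3 counts tuberculosis among the drug's important identified risks, and Course 2 is a second lymphocyte-depleting course. Section 3.4 supports the benefit-risk case by saying that positives are kept from dosing each time. If sites work from 5.4, 5.5.1 and 7.1.8, as they probably will, that measure is not what is delivered: for a latent-only positive, none of these sections requires Course 2 to be withheld. Two sites with the same Month 12 result could act differently, one excluding the subject under 3.4 and the other using the discretion in 5.5.1.

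There is also a reporting consequence. SAP Section 15.3 lists TB and serology positives that do not comply with the protocol. For a latent-TB positive at Month 12, that listing is well defined only if the protocol gives one rule.

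**Working it through.** The question is one of consistency, so the check follows one subject through the text: Month 12, lymphocytes at or above 800 cells/mm³, latent-TB test positive, no active disease.

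1. **Section 3.4:** positive before a dosing schedule, so excluded.
2. **Section 5.4 and the 7.1.8 footnote:** the lymphocyte criterion is met. Nothing here stops Course 2.
3. **5.5.1 mandatory infection item:** the subject has no active TB, so it does not apply.
4. **5.5.1 exclusion-criterion item:** latent TB is in criterion 7, so the item could apply, but only if the Investigator or Sponsor judges discontinuation necessary.
5. **5.5.1 safety item:** it applies only if someone judges the event an unacceptable danger.
6. **5.5.1 latent-infection item:** this has two readings. If it means latent infection, the instruction is to treat and to consider withdrawal or delay, which is a judgement. If it means reactivated disease, it overlaps the mandatory active-TB item and does not reach a latent-only positive. Neither reading makes a mandatory stop.
7. **5.5.1 time limit:** Course 2 is barred only when recovery takes more than 6 months, so dosing after a shorter delay is foreseen.

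Step 1 excludes the subject. Steps 2 to 7 leave the decision to judgement. By contrast, the other Course 2 conditions in 3.4 reach the operative text: the 800 threshold is in 5.4, 5.5.1 and 7.1.8, HIV is in the mandatory list, and hepatitis appears there at least in its active form.

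**Cost of a binding delay rule in lost data.** SAP Section 9 uses 30-day months and treats Course 2 as delayed if it starts more than 360 + 90 + 7 = 457 days after the start of Course 1, or never starts.

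- Delay that keeps the data, counted from day 360: 457 − 360 = 97 days.
- Start at the full 6-month limit, assuming that limit runs from day 360: 360 + 180 = 540 days. This is 540 − 457 = 83 days past the cut-off, or 547 − 457 = 90 days if the 7-day visit window is added.

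Beyond the cut-off, efficacy data count as missing from the start of Course 2. If Course 2 never starts, they count as missing after day 457. Section 5.5.1 gives no start point for its 6 months, so day 360 is an assumption.

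One course is 1.75 / 3.5 = 50% of the cumulative dose. That holds for any Course 2 and does not measure harm. No positive-test rate is given in the documents and none is assumed.

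**The case against.** The strongest reply is that the two sections answer different questions. Section 3.4 bars dosing while the subject is positive; 5.5.1 then decides between withdrawal and delay. On that view a site that doses an untreated positive breaches 3.4, and 5.5.1 nowhere says that Course 2 may be given to such a subject. This is a reasonable way to reconcile the text, and the fix below adopts it. But the protocol does not state it: 3.4 speaks of exclusion rather than deferral, and 5.4, which is headed as the criteria for starting and continuing treatment, omits the condition.

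The protocol also defers to the SmPC for risk minimization, dosing and precautions (3.3, 6.2, 6.5.4). The SmPC may settle the matter for sites. It is not among the documents, so this limits how far the point can be pressed.

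A reader might infer three stronger claims that the documents do not support:

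- *That nothing requires the result before dosing.* Section 3.4 presupposes a known result, and Section 5.2 and Table 3 place testing before Course 2. The SAP has a separate Month 12b visit that anchors the Course 2 schedule. Section 6 ties dispensing to visit registration, but that is supply logistics; it mentions no lymphocyte check either, and the lymphocyte rule plainly applies.
- *That hepatitis B and C have the same gap.* This would depend on how much narrower active hepatitis is than exclusion criterion 6, and the protocol does not define the term.
- *That criteria 6 and 7 should be absolute bars at Month 12.* Criterion 7 has no exemption for completed latent-TB treatment, so an absolute bar would override the treat-or-delay route that 5.5.1 offers.

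**Conclusion.** The inconsistency is in the current text. Section 3.4 gives an unconditional rule for a latent-TB positive before each course, and no operative Course 2 rule makes it binding. It is a minor safety-conduct alignment. The number of subjects is unknown and probably small, because latent TB is excluded at entry, and the primary endpoint is complete before Course 2 begins. The conclusion rests on the protocol and SAP alone; an explicit rule in the SmPC would reduce the practical consequence but would leave the protocol's sections in disagreement.

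**What to change.** Add one sentence to Section 5.4, to the mandatory list in 5.5.1 and to the 7.1.8 footnote: *Course 2 must not be started in a subject with a positive Month 12 latent-TB test until the infection has been adequately treated, and must not be given at all if this takes more than 6 months.* The 6 months is the limit already in 5.5.1; stating when it starts would remove a further ambiguity. Reword the sentence in 3.4 so that, for latent TB, it describes this rule rather than outright exclusion.

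The cost is a protocol clarification and a letter to sites, with no new test or visit. A few subjects may delay or miss Course 2. Those who start more than 457 days after the start of Course 1, or never start, lose later efficacy data under SAP Section 9. Only exploratory analyses after the primary one are touched.
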